#### Best case method (for sensitivity analysis):

The algorithm defined in [Section 10](#) will be used to derive the outcome at 18, 12 and 6 months, with the following changes. The following patients will be considered as **success**:

- Patients lost to follow-up (prior or at visit 18, 12 and 6 months, respectively)
- Patients who refused all post treatment lumbar punctures

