## 5. ANALYSIS SETS AND SUBGROUPS

The analysis sets are defined below:

- **Set of screened HAT positive patients:** All HAT positive patients who signed the informed consent. To be noted that after the 1st DSMB meeting, recruitment of stage 1 and intermediate stage HAT patients was authorized. That will trigger a modification of the initial screened set.
- **Treated set:** all patients who received at least one tablet of acoziborole.
- **Modified Intention-To-Treat (mITT):** All patients who received at least one tablet of acoziborole, excluding patients (\*) who fled the region due to armed conflict or natural disaster or due to force majeure (\*\*) and for whom no failure was detected early (parasite, needs for rescue medication, death or more than 50 WBC/µL in CSF at M6) and no data are available at M12 and M18 due to armed conflict, natural disaster or force majeure affecting the site.
- **Evaluable patients:** Modified Intent-to-treat patients (mITT) and excluding:
  - Patients lost to follow-up at 18 months (for primary efficacy endpoint and secondary efficacy outcome at 18 month), patients lost to follow-up at 12 months (for secondary efficacy outcome at 12 month), patients lost to follow-up at 6 months (for secondary efficacy outcome at 6 month), except those who were a failure before being lost to follow-up (cf. [Section 7.7](#) for programming rules).
  - Patients with no post-treatment lumbar puncture (i.e. patients who refused all lumbar puncture after treatment and who were not a failure)
  - Patients who died for reasons clearly unrelated to efficacy or safety or disease evolution (\*\*).
  - Early consent withdrawal (before M6, i.e. no planned visit attended after 3-month visit).
- **Per Protocol Set (PPS):** Modified Intent-to-treat patients (mITT) with no major protocol deviations (\*\*\*). Major deviations will be described by patient, and exclusion will be decided during the data review (cf. [Section 8.2](#)).

Notes:

(\*) These patients will be included in the Treated set population as failures.

(\*\*) This will be reviewed during data review meeting (e.g. review of comments and reasons of early discontinuation in end-of-study form).

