#### Fair case method (for sensitivity analysis):

The algorithm defined in [Section 10](#) will be used to derive the outcome at 18, 12 and 6 months, with the following changes. Responses of the following patients will be replaced using a **resampling approach**:

- Patients lost to follow-up (prior or at visit 18, 12 and 6 months, respectively)
- Patients who refused all post treatment lumbar punctures
- Patients without WBC in CSF data at the corresponding visit (6, 12 or 18 months, respectively) and no proven success according to prior or posterior visit(s) (see algorithm defined in [Section 10](#) for details)

The resampling will be performed with a **hot deck multiple imputation** method as follows:

- Responses will be replaced by simple random sampling (with replacement) among non-missing responses (=donnors selection)
- The initial seed for random number generation used to select donor units will be set to 495.
- This step will be repeated 100 times in order to produce 100 samples (=number of donor units).
- Each sample will be analyzed as described in section 8.6.1 (i.e. the estimate, its 95% Jeffrey CI and corresponding standard error will be computed for each samples).
- The results of each of these analyses (estimates and standard errors) will be combined using Rubin's rules as implemented in the SAS MIANALYZE procedure to provide combined estimate and the 95% Jeffrey CI.

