## 10. KEY DERIVED VARIABLES

### 10.1. Outcome at 18 months

| Derivation algorithm for stage 1 and intermediate stage (month 18)   | Derivation algorithm for stage 2 (Month 18)  |
|--|--|
| 
Patient is → 1: Dead (any reason of death and any time between drug intake and M18) ⇒ Failure (stop)
         ↓
         Alive
         ↓
 Patient requires rescue medication for HAT at M18 or required it before (between drug intake and M18)
         → YES → 2: (definitive) Failure (stop)
         ↓
         NO rescue medication so far
         ↓
 Evidence of trypanosomes in any body fluid between drug intake and M18 visit ⇒ YES ⇒ 3: (definitive) Failure (stop)
         ↓
         NO observed trypanosomes
         ↓
 Patient Lost to follow-up at M18 (no survival information at M18 and later)
         → YES ⇒ 4: Failure (Stop) [a,b]
         ↓
         NO (the patient is not lost to follow-up)
         ↓
 Non-hemorrhagic lumbar puncture at M18 and WBC in CSF at M18 > 20 cells
         → YES ⇒ 5: Failure (stop)
         ↓
         NO (WBC in CSF at M18 ≤ 20 cells or no reliable data concerning WBC in CSF at M18)
         ↓
 Non-hemorrhagic lumbar puncture at M18 and WBC in CSF ≤ 20 cells
         → YES ⇒ 6: Success (stop)
         ↓
         NO (hemorrhagic CSF sample or no lumbar puncture at M18 for any reason)
         ↓
 No lumbar puncture at M18 or no reliable count of WBC in CSF at M18 but reliable number of WBC in CSF reported later (M24 or other additional visit)
         → YES ⇒ WBC in CSF > 20 ⇒ 7: Failure (Stop)
         → YES ⇒ WBC in CSF ≤ 20 ⇒ 8: Success (Stop)
         ↓
         NO (No lumbar puncture at M18 and no later reliable count of WBC in CSF)
 | 
Patient is → 1: Dead (any reason of death and any time between drug intake and M18) ⇒ Failure (stop)
         ↓
         Alive
         ↓
 Patient requires rescue medication for HAT at M18 or required it before (between drug intake and M18)
         → YES ⇒ 2: (definitive) Failure (stop)
         ↓
         NO rescue medication so far
         ↓
 Evidence of trypanosomes in any body fluid between drug intake and M18 visit ⇒ YES ⇒ 3: (definitive) Failure (stop)
         ↓
         NO observed trypanosomes
         ↓
 Patient Lost to follow-up at M18 (no survival information at M18 and later)
         → YES ⇒ 4: Failure (Stop) [a,b]
         ↓
         NO (The patient is not lost to follow-up)
         ↓
 Non-hemorrhagic lumbar puncture at M18 and WBC in CSF at M18 > 20 cells
         → YES ⇒ 5: Failure (stop)
         ↓
         NO (WBC in CSF at M18 ≤ 20 cells or no reliable data concerning WBC in CSF at M18)
         ↓
 Non-hemorrhagic lumbar puncture at M18 and WBC in CSF ≤ 20 cells
         → YES ⇒ 6: Success (stop)
         ↓
         NO (hemorrhagic CSF sample or no lumbar puncture at M18 for any reason)
         ↓
 No lumbar puncture at M18 or no reliable count of WBC in CSF at M18 but reliable number of WBC in CSF reported later (M24 or other additional visit)
         → YES ⇒ WBC in CSF > 20 ⇒ 7: Failure (Stop)
         → YES ⇒ WBC in CSF ≤ 20 ⇒ 8: Success (Stop)
         ↓
         NO (No lumbar puncture at M18 and no later reliable count of WBC in CSF)
 |

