
| Derivation algorithm for stage 1 and intermediate stage (month 18)   | Derivation algorithm for stage 2 (Month 18)  |
|--|--|
| 
Earlier (before M18) unfavorable outcome: increase of WBC in CSF at M6 or M12 with respect to EOH
 
⇒ YES ⇒ 9: Failure (stop)
 
↓
 
NO (no information or no earlier unfavorable assessment)
 
↓
 
Patient has clinical signs or symptoms at M18 evoking a failure
 
⇒ YES ⇒ 10: Failure (stop)
 
↓
 
NO (no clinical signs or symptoms evoking a relapse at M18)
 
↓
 
WBC in CSF ≤ 20 at M12 or absence of LP at M12 and for both cases no increase WBC in CSF at M6 with respect to EOH and no sign and symptoms at M18 evoking a relapse:
 
⇒ YES ⇒ 11: Success (stop) [b]
 
↓
 
NO (at least one criterion not met)
 
↓
 
Patient refused all post treatment lumbar punctures
 
⇒ YES ⇒ 12: Failure (stop) [a,b]
 
↓
 
All other cases ⇒ 13. Failure
 | 
Earlier (before M18) unfavorable outcome: WBC in CSF > 50 at M6 or WBC in CSF > 20 at M12 or increasing between M6 and M12
 
⇒ YES ⇒ 9: Failure (stop)
 
↓
 
NO (no information or no earlier unfavorable assessment)
 
↓
 
Patient has clinical signs or symptoms at M18 evoking a failure
 
⇒ YES ⇒ 10: Failure (stop)
 
↓
 
NO (no clinical signs or symptoms evoking a relapse at M18)
 
↓
 
WBC in CSF ≤ 20 at M12 or in absence of LP at M12 and for both cases WBC in CSF ≤ 50 at M6 and no signs and symptoms at M18 evoking a relapse:
 
⇒ YES ⇒ 11: Success (Stop) [b]
 
↓
 
NO (at least one criterion not met)
 
↓
 
Patient refused all post treatment lumbar punctures
 
⇒ YES ⇒ 12: Failure (Stop) [a,b]
 
↓
 
All other cases ⇒ 13. Failure
 |

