**For sensitivity analyses:**

[a] will be considered as a success with the best case method (see [Section 7.6.1](#)).

[b] re-sampling will be applied with the fair case method (see [Section 7.6.1](#)).

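### The best-case and fair-case analyses make no exception for stage 2 patients lost after a CSF count that SAP 10.1 itself treats as unfavourable

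*SAP*

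**What the plan says.** Steps are numbered as in the stage 2 column of SAP 10.1.

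- Steps 1 to 3: death, rescue medication, or trypanosomes at any time up to month 18 give failure. None carries a flag.
- Step 4: a patient lost at month 18 ("no survival information at M18 and later") is a failure, flagged [a,b]. The algorithm stops there. Under SAP 7.7, loss at month 18 is a tick on the End of Study form, so the month 6 and month 12 visits may have taken place.
- Steps 5 to 8: a reliable CSF count at month 18, or failing that a later one, decides the outcome. Above 20 is failure; 20 or below is success.
- Step 9: "Earlier (before M18) unfavorable outcome", defined for stage 2 as more than 50 cells at month 6, more than 20 at month 12, or a rise between the two, is a failure. It carries no flag.

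The notes below the algorithm say that outcomes flagged [a] "will be considered as a success with the best case method" and that outcomes flagged [b] are resampled in the fair case.

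SAP 7.6.1 gives the best-case list, including "Patients lost to follow-up (prior or at visit 18, 12 and 6 months, respectively"), and the fair-case list. The third fair-case item is "Patients without WBC in CSF data at the corresponding visit" "and no proven success according to prior or posterior visit(s"), with a reference to Section 10 for details. The fair-case draw is unconditional: "Responses will be replaced by simple random sampling (with replacement) among non-missing responses".

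SAP 5 treats earlier failure differently. The Evaluable set removes lost patients but keeps those who had failed before loss. The mITT definition drops patients who fled conflict, disaster or force majeure only if, among other conditions, "no failure was detected early (parasite, needs for rescue medication, death or more than 50" WBC/µL at month 6.

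**The concern.** Sensitivity analyses #4 and #5 are meant to show how far missing outcomes could move the 18-month success rate. As ordered, the algorithm discards an unfavourable CSF count once the patient is lost, and the replacement rule then ignores it. Yet that count is informative by the plan's own account. Protocol Table 1 classes 50 cells or more at month 6 as probable relapse, and SAP 8.6.1.4 lists the month 6 and month 12 counts among the variables that explained the 18-month outcome in earlier data.

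Two patients with the same relapse-level count and no later reliable count can therefore be scored differently, with the lost patient scored more favourably. The conflict between the third fair-case bullet and the flags is a separate problem: two programmers could obtain different fair-case results.

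**Working it through.** **Tracing four stage 2 patients.** Each has 80 cells/µL at month 6 and no death, rescue or trypanosomes.

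| Patient | Stops at | Primary | Best case (#5) | Fair case (#4) |
|---|---|---|---|---|
| Lost before month 18 | Step 4 [a,b] | Failure | Success | Random draw |
| Attends month 18, no reliable count then or later | Step 9, no flag | Failure | Failure | Failure by the flags; redrawn by the third bullet |
| Attends, reliable count 20 or below at month 18 | Step 6 | Success | Success | Success |
| No reliable month 18 count, later reliable count 20 or below | Step 8 | Success | Success | Success |

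The anomaly lies between the first two rows only.

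**Other algorithms.** The stage 1/intermediate column has the same order, with step 9 defined as a rise over the end-of-hospitalisation count. SAP 10.2 also tests loss at step 4, before it uses the month 6 count. SAP 10.3 has no counterpart: under SAP 7.7 a patient lost at month 6 has no visit at month 6 or later, and no routine puncture is planned at month 3.

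**The plan's own intervals** (protocol 9.1, Jeffreys, 155 patients). Quantiles of Beta(x+0.5, n−x+0.5) give 83.4–93.2% for 138/155 and 89.7–97.1% for 146/155. Both match the plan. The lower arms are 89 − 83.4 = 5.6 points and 94 − 89.7 = 4.3 points.

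**Effect per patient.**

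- Best case: 1/155 = 0.65 points.
- Fair case: r/155, where r is the donor success rate. The documents give no r. At 89% it is 0.89/155 = 0.57 points; at 97% it is 0.97/155 = 0.63. If the patient kept as a failure also joins the donors, the figure can reach 0.64 (below).
- Stage 1/intermediate cohort, about 50 patients planned: 1/50 = 2 points in the best case.

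**Illustration.** S is the number of primary successes, L the number lost and k the number lost after an unfavourable count. L and k are assumptions.

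- Best case: (S+L)/155 now, (S+L−k)/155 with the exception.
- Expected fair case: (S + L·S/(155−L))/155 now, (S + (L−k)·S/(155−L+k))/155 with the exception.

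With L = 5:

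| S | k | Best case now | With exception | Fair case now | With exception |
|---|---|---|---|---|---|
| 138 | 1 | 92.3% | 91.6% | 92.0% | 91.4% |
| 138 | 3 | 92.3% | 90.3% | 92.0% | 90.2% |
| 138 | 5 | 92.3% | 89.0% | 92.0% | 89.0% |
| 146 | 1 | 97.4% | 96.8% | 97.3% | 96.7% |
| 146 | 3 | 97.4% | 95.5% | 97.3% | 95.4% |
| 146 | 5 | 97.4% | 94.2% | 97.3% | 94.2% |

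For S = 146 and k = 1, the unrounded fair-case figures are 97.33% and 96.69%, a difference of 0.64 points. For k = 3, the best-case lower bound falls from 87.3% to 84.9% (S = 138) and from 94.0% to 91.3% (S = 146).

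**The case against.** The strongest reply is that a best case is an upper bound by design. The lost patient's month 18 status is unknown and could have been a success at step 6. The plan does not treat these counts as final: SAP 6.3 requires later confirmation of more than 50 cells at month 6 or more than 20 at month 12, and Protocol Table 1 never calls a count alone a proven relapse. This has weight for #5, less for #4, which is not a bound. Nor is #5 a consistent bound, since it leaves the step 9 attender a failure.

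The affected group is also narrow. Patients with death, rescue or parasites stay failures at steps 1 to 3, and a suspected relapse prompts a return visit (protocol 6.4.4) and, if confirmed, rescue treatment (protocol 5.4). The Evaluable-set analysis (#2) already keeps earlier failures, and no success threshold depends on #4 or #5. All of this stands and limits the importance of the point.

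A reader might infer more than the documents support:

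- That anyone with the same count who attends month 18 stays a failure. Steps 6 and 8 make such a patient a success on a reliable count of 20 or below.
- That the fair-case contrast is certain. It holds under the Section 10 flags. If the third bullet governs, the attender is redrawn too; the contrast disappears, but a second group with unfavourable counts loses its failure status.
- That the SAP flatly contradicts itself through its mITT definition. That wording decides who leaves the analysis set, not the outcome in every analysis. It shows how the authors regard such a count, no more.

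**Conclusion.** The point holds for sensitivity analyses #4 and #5 and their versions for other endpoints and cohorts that use the same order. They lack an exception for failure before loss that the SAP applies elsewhere, and the third fair-case bullet disagrees with the absence of a [b] flag on step 9.

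It does not touch the primary analysis, where these patients are failures. It should not be read as bias in the main result.

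The effect is 0.65 points per patient in the best case and about 0.57 to 0.64 in the fair case, for 155 stage 2 patients and an assumed donor success rate of 89% to 97%. A single donor rate such as 95% is plausible but not given in the documents. Three affected patients, an assumed number, would move the best case by 3/155 = 1.9 points, against lower interval arms of 4.3 to 5.6 points. One patient would matter little, and there may be none.

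**What to change.** 1. In SAP 7.6.1, for the best-case and fair-case methods only, add the Evaluable-set exception with an explicit criterion: a stage 2 patient lost after more than 50 cells at month 6 or more than 20 at month 12 stays a failure. At step 4 of SAP 10.1, keep [a,b] for the other lost patients only.
2. Do not import step 9 whole. Its third limb, any rise between months 6 and 12, would make a patient going from 2 to 4 cells a fixed failure even in the best case.
3. State the matching criterion for the stage 1/intermediate column. For SAP 10.2 state one based on the month 6 count alone, because a patient lost at month 12 has no month 12 count. The thresholds do not carry over directly: for stage 2 the 10.2 fallback uses more than 20 at month 6, whereas 10.1 uses more than 50.
4. Align the third fair-case bullet with the [b] flags, so that steps 9 and 10 of SAP 10.1 are not redrawn.
5. Leave the observed-case analysis (#6) as it is, with missing month 18 data treated as missing.

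The cost is SAP wording and one extra check in the derivation, with no new data. The best-case and fair-case figures become slightly less favourable if any such patient exists.

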#### Observed case method (for sensitivity analysis):

The algorithm defined in [Section 10](#) will be used to derive the outcome at 18, 12 and 6 months, with the following changes. The following patients will be considered as having a **missing** outcome:

- Patients with missing data at visit 18, 12 and 6 months, respectively.

### 7.6.2. Handling of intercurrent events

The handling of post-treatment intercurrent events such as rescue medication intake, death, early consent withdrawal, lumbar puncture refusal, study discontinuation including war and natural disaster are taken into account in the algorithm for determining the outcome and in population definitions. Concomitant therapies other than rescue medication are not taken into account in the assessment of efficacy.

### 7.6.3. Handling of missing AE attributes

Missing relationship, missing seriousness, and/or missing severity will not be replaced and will be analysed as such. Onset date of AE will be imputed as below. The objective is to maximize the probability the AE is considered as treatment-emergent.

|                           |  |
|---------------------------|--|
| Onset date of AE          | Imputed AE onset date  |
| Completely missing        | Date of first study drug administration  |
| Day is missing            | First day of the month.

If imputed date is prior to first study drug administration, then replace with date of first study drug administration. |
| Day and month are missing | First of January.

If imputed date is prior to first study drug administration, then replace with date of first study drug administration.       |

Note: partially or completely missing end dates of AE will not be imputed.

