## 6.4. Safety endpoints

### 6.4.1. Adverse events

The following AE categories will be studied:

- All AEs collected during the study
- All AEs occurring before the intake of the study drug (i.e. from D-15 to D-1)
- Treatment-emergent adverse events (TEAE) occurring:
  - During the follow-up period (i.e. from D1 to 18 months)
  - The day of the intake of the study drug (i.e. D1)
  - During the hospitalization period (i.e. from D2 to D15)
  - Post-hospitalization period (i.e. from D16 to 18 months)
- Mild/moderate TEAE (grade 1, grade 2, mild or moderate)
- Severe TEAE (grade 3, grade 4, grade 5 or severe)
- Drug-related TEAE occurring:
  - During the follow-up period (i.e. from D1 to 18 months)
  - The day of the intake of the study drug (i.e. D1)
  - During the hospitalization period (i.e. from D2 to D15)
  - Post-hospitalization period (i.e. from D16 to 18 months)
- Serious TEAE
- Serious drug-related TEAE
- TEAE of interest

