#### Definition of treatment-emergent AEs:

Treatment-emergent AEs are defined as any AE which occurs on or after the date of study-drug administration or which worsen in intensity on or after the date of study-drug administration.

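### The partial-date rule for adverse events puts some onsets already recorded as pre-dose on the dosing date and so counts them as Day 1 treatment-emergent (minor)

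*SAP*

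**What the plan says.** SAP 7.6.3 handles incomplete onset dates in three cases. A fully missing onset becomes the dosing date. A missing day becomes the first of the month. For the third case the table reads "Day and month are missing | First of January". The last two cases carry the same further step: "If imputed date is prior to first study drug administration, then replace with date of first study drug administration". The purpose is given as "The objective is to maximize the probability the AE is considered as treatment-emergent". On end dates the section says only that "partially or completely missing end dates of AE will not be imputed"; the onset rule makes no use of an end date that was recorded.

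SAP 6.4.1 counts as treatment-emergent "any AE which occurs on or after the date of study-drug administration", and also an event that gets worse in intensity from that date on. It sets up separate reporting categories for "All AEs occurring before the intake of the study drug (i.e. from D-15 to D-1)" and for treatment-emergent events on "The day of the intake of the study drug (i.e. D1)". The display plan gives each its own table: 14.3.1.3.1 for pre-dose events and 14.3.1.3.2 for Day 1.

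Protocol 6.5.4 collects serious events from consent. It records non-serious events before dosing only if they may be linked to taking part in the study. Protocol 6.2.2 and 6.2.3 and the schedule of events list adverse event collection at screening and baseline without that limit.

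**The concern.** A conservative imputation rule should settle cases that the data leave open. This one also reverses cases that the data have settled. If the recorded month, or the recorded year when that is all there is, ends before dosing, the onset was before dosing wherever the missing day falls. The replacement step overrides that. It then feeds a definition of treatment emergence that turns on onset relative to dosing.

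A recorded stop date is ignored in the same way. An event that ended before dosing, with its onset date missing or given only as the dosing month, receives an onset later than its own end.

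What is at stake is the split between the pre-dose table and the treatment-emergent tables, above all the Day 1 table. The trial has one dose and no control arm, so no comparator would show the same artefact. A misplaced serious event would also enter the serious treatment-emergent tables.

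**Working it through.** The plan states no figure to reproduce here, so the check applies the printed rule to dates.

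**The rule as a formula.** For a partial date, imputed onset = the later of (first of the recorded month, or 1 January of the recorded year) and the dosing date. The result is never before dosing. Under the printed rule, no partially dated event can be classed as pre-dose by its onset date.

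**Worked dates.**

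| Dosing | Recorded onset | First imputation | After replacement | What the recorded part shows |
|---|---|---|---|---|
| 10/06/2018 | --/05/2018 | 01/05/2018 | 10/06/2018, Day 1 | Onset before dosing |
| 08/01/2018 | --/12/2017 | 01/12/2017 | 08/01/2018, Day 1 | Onset before dosing |
| 08/01/2018 | 2017 | 01/01/2017 | 08/01/2018, Day 1 | Onset before dosing |
| 08/01/2018 | --/01/2018 | 01/01/2018 | 08/01/2018, Day 1 | Open |
| 08/01/2018 | 2018 | 01/01/2018 | 08/01/2018, Day 1 | Open |
| 08/01/2018 | --/02/2018 | 01/02/2018 | 01/02/2018, not moved | Onset after dosing |

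The first row lies within the screening window: there is no Day 0, so for dosing on 10/06/2018, D-15 is 26/05/2018. Had the site written 31/05/2018, the same event would be pre-dose. Losing the day changes the class although the month alone decides it.

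**Stop date.** Dosing 10/06/2018, onset --/06/2018, stop 05/06/2018: the first imputation is 01/06/2018 and the replacement is 10/06/2018, five days after the event ended.

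**How often the recorded part settles the matter.** Assume that dosing dates are spread evenly over 2017–2020 and pre-dose onsets evenly over D-15 to D-1.

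- Pairs of dosing date and pre-dose day: 1,461 × 15 = 21,915.
- For dosing on day m of a month (m = 1 to 15), 16 − m of the 15 pre-dose days fall in the previous month. The sum over m is 15 + 14 + … + 1 = 120 per month, and over 48 months 48 × 120 = 5,760. Share in an earlier month: 5,760 / 21,915 = 26.3%.
- Earlier year (January dosing only): 4 × 120 = 480, and 480 / 21,915 = 2.2%.
- Dosing dates whose full 15-day window touches an earlier month: 48 × 15 / 1,461 = 720 / 1,461 = 49.3%.

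Among pre-dose events with a partial onset date, the printed rule classes 100% as treatment-emergent. A rule that requires the recorded part to match dosing would class 73.7% so when the month is known (100 − 26.3) and 97.8% when only the year is known (100 − 2.2). Those remaining cases are the open ones.

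**Size per event.** Safety is analysed on the Treated set (SAP 8.8). Planned totals are 155 + 50 = 205, or 162 + 50 = 212 if all the replacement provision is used. One patient is 1/205 = 0.49 points or 1/212 = 0.47 points overall, and 1/50 = 2 points in cohort 2. These are upper bounds, because a percentage of patients with at least one event moves only if that patient has no other event in the row.

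**The case against.** The strongest defence is that the rule does what it announces. The SAP's declared aim is to maximise treatment-emergent classification without qualification, and the error runs against the sponsor's own drug. That supports the dosing date wherever timing is open: a fully missing onset, or a recorded month or year equal to that of dosing. It does not support overriding a recorded month or year that already places the onset before dosing.

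Four further points stand and limit the finding.

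- Onset before dosing does not by itself make an event pre-treatment, because SAP 6.4.1 also counts worsening from dosing onward. Any correction must keep that route open, or it would hide real treatment-emergent events.
- The exposed set is narrow. Under protocol 6.5.4, non-serious screening events are recorded only if they may be linked to participation. Screening lasts at most 15 days, and protocol 11.7 has data queries raised and resolved throughout.
- A reader might infer from the 49.3% that about half of the partially dated pre-dose events are affected. That figure counts dosing dates whose full window touches an earlier month. The share of pre-dose days in an earlier month is 26.3%.
- A reader might also infer that the moved events would be reported as acute drug reactions. The documents do not support this. Causality is the investigator's judgement (protocol 6.5.7), imputation does not alter it, and drug-related Day 1 events have their own table (14.3.1.4.1), which an event judged not related does not enter. All events are also listed individually (SAP 8.8.1).

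**Conclusion.** The rule is wrong as written, and the consequence is minor. It misclassifies pre-dose serious events and recorded screening events that lack an onset day and carry an earlier month or year, or whose recorded stop date precedes dosing, unless they worsened on or after dosing. These events leave the pre-dose table and enter the all-causality treatment-emergent and Day 1 tables.

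The documents give no count of partial dates, so the number is unknown; it is probably very small and could be zero. The 26% and 2% shares rest on the assumption of uniform dates. They describe the fraction of partially dated pre-dose events settled by the month or by the year, not a fraction of all events. Each misplaced event is worth at most about 0.5 points overall or 2 points in cohort 2.

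The efficacy analyses are untouched and recorded causality is unchanged. The finding does not show that the safety profile would be materially distorted.

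**What to change.** In SAP 7.6.3, make the replacement conditional:

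- Use the dosing date only if the onset is fully missing, or its recorded month and year (or the year alone, if the month is missing) equal those of dosing, and in either case no recorded stop date is before dosing.
- If the recorded month or year, or the recorded stop date, is before dosing, keep the onset as pre-treatment. The exception is an event that worsened in intensity on or after dosing, which remains treatment-emergent under SAP 6.4.1.

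Assign these events to the pre-dose table by a flag and not by the imputed day, since a first-of-month date such as 01/05/2018 can fall before D-15.

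The cost is a few sentences in the SAP and a small change to the onset-date program. No new data are needed. Every date that is truly open still counts as treatment-emergent, so the conservative aim is kept.
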